### **4.3 Withdrawal Criteria**

A subject may prematurely discontinue study drug and/or withdraw from the study at any time. A distinction must be made between premature discontinuation of study drug and withdrawal from the study. A subject may prematurely discontinue study drug and still continue his/her participation in the study. Subjects who prematurely discontinue study drug dosing will be encouraged to continue in the study and complete visits and procedures as per Protocol.

The reasons for premature discontinuation of study drug and for withdrawal from the study must be documented in the electronic case report form (eCRF). Reasons include, but are not limited to, the following:

- Withdrawal of consent;
- Any event, laboratory abnormality, intercurrent illness, or other medical condition that indicates to the Investigator that continued participation is not in the best interest of the subject;
- Pregnancy;
- Subject failure to comply with Protocol requirements or study-related procedures;
- Termination of the study by the Sponsor or regulatory authority;
- Initiation of any prohibited medication(s) as described in [Section 5.6.1](#);
- Severe allergic reactions to the study drug; or
- Any stopping rule as described in [Section 3.2](#).

If a subject withdraws prematurely from the study for any reason, study staff should make every effort to complete the full panel of assessments scheduled for Day 8/ET. The reason for subject withdrawal must be documented in the eCRF.

In the case of a subject lost to follow-up, attempts to contact the subject must be made and documented in the subject's records.

Withdrawn subjects may be replaced at the discretion of the Sponsor. Subjects who discontinue for study drug-related safety or tolerability reasons will not be replaced.

#### **4.4 Reserve Subjects**

The population for this study is healthy subjects. Additional subjects will be screened as reserve subjects for each treatment group. Reserve subjects who are eligible for enrollment will also be admitted to the CPU to ensure enough eligible subjects are available to fill the treatment group. Results of study admission procedures from Day -1 are not required to be repeated, provided the subject remains domiciled, and Protocol restrictions are monitored and followed.

Reserve subjects who fall outside of the Screening Period window will be allowed to rescreen. In addition, subjects who fail to qualify at Screening due to use of a prohibited medication may be permitted to rescreen if medication usage changes. Subject eligibility may also be reassessed if there is a change in eligibility procedures or criteria.

## 5 STUDY TREATMENTS

### 5.1 Treatment Groups

The study is planned to include 3 parallel treatment groups, with 40 subjects randomized in a 3:3:2 ratio to receive ROSE-010 99 mcg, ROSE-010 150 mcg, or placebo, respectively, as follows:

- Treatment Group 1: 99 mcg ROSE-010 (15 subjects) administered SC once daily for 7 consecutive days;
- Treatment Group 2: 150 mcg ROSE-010 (15 subjects) administered SC once daily for 7 consecutive days; and
- Treatment Group 3: Placebo (10 subjects) administered SC once daily for 7 consecutive days.

### 5.2 Rationale for Dosing

The rationale for selection of the ROSE-010 dose levels (99 mcg and 150 mcg) is based on the results of Clinical Studies GL61-001, RP-09-01, and RP-23-01 (see [Section 1.3](#) and the ROSE-010 Investigator's Brochure).

The results from Study RP-09-01 showed that 300 mcg and 100 mcg have observable effects on gastric emptying relative to placebo which is known to be directly related to appetite reduction. Nausea and vomiting, known side-effects of GLP-1 treatment, were more frequently reported with the higher dose (300 mcg). The dose selection was confirmed as relevant by the results from the RP-23-01 study. In this study, a trend in dose dependency was noted as well as a decrease overall in food intake relative to placebo with tolerable nausea.

In Study GL61-001 there was no difference in pain relief response 1 hour post-dose between the dose groups 100 and 300 mcg, which were both significantly different from placebo. At 2 hours post-dose, the pain relief response was observed to diverge between the treatment groups with a difference of approximately 10 mm on the visual analogue scale (VAS) (0 to 100 mm). Both groups were significantly superior to placebo at 2 hours post-dose.

In Study RP-23-01, 14 male and female subjects were randomized to receive a sequence of placebo, 100 mcg ROSE-010, and 150 mcg ROSE-010. Eleven subjects completed all 3 treatment periods. There was a signal indicating a possible dose dependency in amount of food consumed, suggesting that ROSE-010 may have a role in weight management and obesity. No safety concerns were raised.

Nausea and vomiting were both more frequently reported with higher dose.

These data show the following:

- There is no difference in pain relief response at 1 hour post-dose between ROSE-010 100 mcg and 300 mcg; and
- The occurrence of the side effects nausea and vomiting is dose dependent with Studies RP-09-01 and GL61-001 showing approximately double the frequency of vomiting in the case of 300 mcg compared with 100 mcg.

In summary, the doses of ROSE-010 99 mcg and 150 mcg are justified as being within a pharmacologically effective range but with a lower risk for side effects as compared to 300 mcg.

### **5.3 Randomization and Blinding**

Subjects meeting eligibility criteria at Screening and Check-In will be randomized prior to study drug administration on Day 1 in a 3:3:2 ratio to ROSE-010 99 mcg, ROSE-010 150 mcg, or placebo, respectively. Randomization assignments will be provided by the Medpace Biostatistics Department. Following randomization, study drug will be dispensed in a double-blind manner. The Sponsor and all site personnel except the unblinded Pharmacist, unblinded pharmacy staff, and unblinded Clinical Research Associate (CRA), if assigned, will be blinded to the treatment group for each subject. Subjects will also be blinded to the treatment they receive.

Bioanalytical staff involved in analysis of PK samples will be unblinded to treatment either via receipt of the randomization code to allow for analysis of samples from subjects receiving ROSE-010 only, or by the nature of the results of sample analysis.

### **5.4 Breaking the Blind**

Blinding is not to be broken during the study unless considered necessary by the Investigator for emergency situations for reasons of subject safety or by the Sponsor based on safety and tolerability and/or PK data. Unblinding at the CPU for any other reason will be considered a Protocol deviation. The Investigator should contact the Medical Monitor before breaking the blind if time permits. When the blind is broken, the reason must be fully documented. The Pharmacist at the CPU will inform the Investigator of the treatment assignment via the randomization schedule held in the pharmacy.

### **5.5 Drug Supplies**

#### **5.5.1 Formulation and Packaging**

ROSE-010 (300 mcg/mL) is a clear, colorless, aqueous, sterile solution for SC injection and will be provided in 2R injection vials. Each vial contains 1 mL ROSE-010 and is for single use.

Commercially available sterile normal saline (0.9% NaCl) solution for injection will be used as the placebo.

#### **5.5.2 Study Drug Preparation and Dispensing**

Individual doses of ROSE-010 or matching placebo will be prepared by the unblinded pharmacy staff and dispensed by the Pharmacist at the clinical site in a blinded manner.

#### **5.5.3 Study Drug Administration**

Study drug (ROSE-010 [99 mcg or 150 mcg] or placebo) will be administered as a single SC injection once daily (30 minutes before lunch) for 7 consecutive days (Days 1 to 7). Study drug will be administered by blinded clinical staff who are trained, qualified, and designated by the Investigator. All doses will be administered SC in the abdominal skin; the injection site location in the abdomen will be rotated at each administration.

#### **5.5.4 Treatment Compliance**

To ensure treatment compliance, all doses will be administered under the supervision of study site personnel. The route, location, date, and time of each study drug administration will be recorded in the source documentation for each subject.

### 5.5.5 Storage and Accountability

Study drug must be stored in a pharmacy or a locked, secure storage facility, accessible only to those individuals authorized by the Investigator to dispense the drug.

Bulk ROSE-010 vials are stable when stored at the recommended storage conditions of 2 to 8°C and protected from light. The doses will be prepared by unblinded pharmacy staff on the day of administration in close proximity to dose administration.

Normal saline used as placebo should be stored in accordance with the package insert.

Records will be maintained indicating the receipt and dispensation of all study supplies. At the conclusion of the study, any unused study drug will be destroyed on site or returned to the Sponsor or designee for final drug accountability and destruction. A certificate of destruction will be provided. If no study drug remains, this will be indicated in the Drug Accountability Log.

The site Pharmacist will perform an ongoing inventory of study drug on behalf of Rose Pharma. The responsible Pharmacist at the site must keep accurate records of all study drug received, amount used/dispensed per subject, and amount returned/disposed, as well as a temperature log to document temperature conditions during storage. A full reconciliation of drug inventory will be performed after the study has completed and the results of the inventory will be checked against the Drug Accountability Log.

## 5.6 Prior and Concomitant Medications and/or Procedures

### 5.6.1 Excluded Medications and/or Procedures

Subjects with the following medications and procedures will be excluded:

- Any prescribed or OTC medication other than approved contraceptives (see [Inclusion Criterion 6](#)) within 14 days or 5 half-lives (whichever is longer) prior to dosing on Day 1 and throughout the study;

Note: Following study drug administration, medications used for the treatment of AEs may be allowed at the discretion of the Investigator or designee.

- Any GLP-1 receptor agonist, GLP-1/glucose-dependent insulintropic polypeptide dual agonist (eg, tirzepatide), or any prescription or OTC medications intended for weight loss or with a potential impact on weight and appetite regulation (eg, stimulant medications) within 6 months of Screening;
- Previous bariatric surgery, procedure for obesity, or GI surgery altering GI passage, motility, and/or nutrient absorption;
- Surgical procedures within 4 weeks of Check-In or planned elective surgery during the study period;
- Blood donation  $\geq 500$  mL within 8 weeks prior to Screening, blood transfusion/severe blood loss within 3 months prior to Screening; and
- Actively participating in an experimental therapy study; or received experimental therapy with a small molecule within 30 days of the first dose of study drug or 5 half-lives, whichever is longer; or received experimental therapy with a large molecule within 90 days of the first dose of study drug or 5 half-lives, whichever is longer.

#### 5.6.2 Restricted Medications and/or Procedures

Following study drug administration, medications used for the treatment of AEs may be allowed at the discretion of the Investigator or designee.

#### 5.6.3 Allowed Medications and/or Procedures

Medically accepted contraceptive methods are permitted as outlined in [Inclusion Criterion 6](#).

#### 5.6.4 Lifestyle Restrictions

Subjects must not have a history of alcoholism or drug/chemical abuse within 12 months prior to Screening or be unwilling to abstain from alcohol and drugs throughout the study. Subjects must not have a typical consumption of  $\geq 14$  alcoholic drinks weekly. Subjects must not use tobacco- or nicotine-containing products (including vaping devices) within 6 months prior to Screening and throughout the study. Subjects must refrain from strenuous exercise from 4 days prior to Day 1 until discharge from the CPU on Day 8.

#### 5.6.5 Documentation of Prior and Concomitant Medication Use

Any treatment or medication (including nutritional supplements) or procedure administered from the time of informed consent and throughout the study is considered a concomitant medication/procedure. This includes medications that were started before the study and are ongoing during the study. Any concomitant procedures/medications will be documented in the appropriate eCRF. Any medications administered within 6 months prior to the first dose of study drug and during the study must be recorded in the eCRF.

## **6 STUDY PROCEDURES**

Study procedures will follow the Schedule of Events ([Appendix A](#)).

## **7 EFFICACY AND PK ASSESSMENTS**

### **7.1 Endpoints**

#### **7.1.1 Primary Endpoint**

The primary endpoint is the amount of food (weight and energy content) consumed during lunch on each day of treatment (Day 1 to Day 7) after administration of ROSE-010 at 2 dose levels (99 mcg and 150 mcg) compared to placebo.

#### **7.1.2 Secondary Endpoints**

The secondary endpoints are the following:

- Hunger score on a VAS (0 to 100 mm) measured pre-dose; 20 minutes after study drug administration; and 1.5, 2.5, 3.5, 4.5, 5.5, and 6.5 hours after study drug administration;
- Satiety score on a VAS (0 to 100 mm) measured pre-dose; 20 minutes after study drug administration; and 1.5, 2.5, 3.5, 4.5, 5.5, and 6.5 hours after study drug administration;
- Prospective consumption score on a VAS (0 to 100 mm) measured pre-dose; 20 minutes after study drug administration; and 1.5, 2.5, 3.5, 4.5, 5.5, and 6.5 hours after study drug administration;
- Desire to eat score on a VAS (0 to 100 mm) measured pre-dose; 20 minutes after study drug administration; and 1.5, 2.5, 3.5, 4.5, 5.5, and 6.5 hours after study drug administration;
- Palatability (tastiness) score on a VAS (0 to 100 mm) measured at the start of lunch;
- Incidence and severity of nausea on a VAS (0 to 100 mm) measured pre-dose; 20 minutes after study drug administration; and 1.5, 2.5, 3.5, 4.5, 5.5, and 6.5 hours after study drug administration; and
- Plasma PK analysis of ROSE-010: maximum plasma concentration ( $C_{max}$ ), time to  $C_{max}$  ( $T_{max}$ ), area under the plasma concentration-time curve (AUC), terminal phase elimination half-life ( $t_{1/2}$ ), and other plasma PK parameters.

#### **7.1.3 Exploratory Endpoint**

The exploratory endpoint is the effect of 7 days of treatment with ROSE-010 on body weight, measured as the relative change (ie, percent change) in body weight from baseline to Day 8.

### **7.2 Clinical Efficacy Assessments**

#### **7.2.1 Amount of Food Consumed (Weight and Energy Content)**

The start time of the standardized lunch will be 30 minutes post-dose; start time will be recorded. Subjects will consume as much of the standardized lunch as desired, and food will be weighed prior to and after eating to assess food intake.

#### **7.2.2 Efficacy Visual Analogue Scales**

On Days 1 through 7, the VAS questionnaire to evaluate hunger, satiety, prospective consumption, and desire to eat will be administered pre-dose; 20 ( $\pm 5$ ) minutes after study drug administration;

and 1.5, 2.5, 3.5, 4.5, 5.5, and 6.5 hours ( $\pm 5$  minutes) after study drug administration. On Day -1, the VAS questionnaire to evaluate hunger, satiety, prospective consumption, and desire to eat will be administered 10 ( $\pm 5$ ) minutes prior to the start of lunch and 1, 2, 3, 4, 5, and 6 hours ( $\pm 5$  minutes) after the start of lunch. On Day -1 and on Days 1 through 7, the VAS questionnaire to evaluate palatability will be administered at the start of lunch (see [Appendix A](#)). For details regarding the VAS questionnaire to evaluate nausea, which is a safety assessment, see [Section 8.14](#). VAS questionnaires are provided in [Appendix C](#).

#### 7.2.2.1 Hunger

Hunger will be assessed by the subject using a VAS graded from 0 to 100 mm with 0 mm corresponding to “not hungry at all” and 100 mm corresponding to “extremely hungry”.

#### 7.2.2.2 Satiety

Satiety will be assessed by the subject using a VAS graded from 0 to 100 mm with 0 mm corresponding to “not full at all” and 100 mm corresponding to “extremely full”.

#### 7.2.2.3 Prospective consumption

Prospective consumption will be assessed by the subject using a VAS graded from 0 to 100 mm with 0 mm corresponding to “nothing at all” and 100 mm corresponding to “a large amount”.

#### 7.2.2.4 Desire to eat

Desire to eat will be assessed by the subject using a VAS graded from 0 to 100 mm with 0 mm corresponding to “no wish to eat at all” and 100 mm corresponding to “extreme wish to eat”.

#### 7.2.2.5 Palatability

Palatability will be assessed by the subject using VASs for odor, taste, and texture graded from 0 to 100 mm with 0 mm corresponding to “not pleasant at all” and 100 mm corresponding to “extremely pleasant”.

### 7.2.3 Change in Body Weight

Body weight should be measured while the subjects are wearing a gown or light indoor clothing without shoes, while fasting for at least 10 hours, and after voiding. Body weight measurements should be done in a consistent manner using a calibrated electronic scale capable of measuring weight in kilograms to 1 decimal place. Body weight will be assessed at Screening, Check-In, and Day 8/ET, as indicated in the Schedule of Events ([Appendix A](#)).

## 7.3 PK Assessments

Blood samples will be collected to evaluate PK at the times indicated in the Schedule of Events ([Appendix A](#)). The actual date and time of collection of each PK sample will be recorded.

The following plasma PK parameters will be determined for ROSE-010 following SC administration on Day 1, as the data permit:

- $C_{max}$ ;
- $T_{max}$ ;

- AUC from Day 1 to infinity; and
- AUC from time 0 to the time of the last measurable concentration ( $AUC_{0-t}$ ).

The following plasma PK parameters will be determined for ROSE-010 following the final dose on Day 7, as the data permit:

- $C_{max}$ ;
- Plasma trough concentration;
- $T_{max}$ ;
- AUC over a dosing interval;
- $AUC_{0-t}$ ;
- $t_{1/2}$ ;
- Apparent first-order terminal elimination rate constant;
- Apparent plasma clearance;
- Observed accumulation index for  $C_{max}$  and AUC;
- Average concentration over the dosing interval  $\tau$ ;
- Swing; and
- Percent fluctuation (fluctuation %).

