### **1.1 Background**

ROSE-010 is a 31 amino acid peptide identical to native GLP-1 (7-37) but position 8 has been substituted by valine, which renders the molecule resistant to dipeptidyl peptidase IV degradation. This amino acid substitution results in a prolonged circulating half-life of approximately 1 hour in the human following subcutaneous (SC) injection. ROSE-010 is identical to LY307161, a product previously under development by Eli Lilly and Company for the treatment of type 2 diabetes mellitus (T2DM).

Following the launch of the first GLP-1 drugs to treat diabetes it became clear that they had a significant effect on weight loss. As obesity and overweight are risk factors for T2DM, this was seen as a positive outcome. The effect on weight loss is due to appetite reduction and not due to increase in energy output. These clinical observations in diabetes patients, backed up by clinical studies in obese patients, led to approvals of GLP-1 drugs for weight loss in 2021.

The main side effects of all GLP-1 drugs are nausea and vomiting, and the continuous exposure to GLP-1 activity in order to maintain the weight target gives rise to continuous side effects. Rose Pharma believes that ROSE-010 may be an attractive option for overweight or obese patients who discontinue use of the longer acting versions due to persistent and continuous gastric side effects such as nausea.

ROSE-010 is fast acting and starts to exert its effects within 30 minutes with a plasma half-life of about 1 hour and its effects diminish within a few hours, making it ideally suited for administration around the main meal of the day.

ROSE-010 is being developed for indications where GLP-1 is implicated in the underlying physiology such as weight management, obesity, and gastrointestinal (GI) disturbances including irritable bowel syndrome (IBS).

Rose Pharma is now initiating clinical studies with ROSE-010 to investigate the preliminary efficacy on appetite and food intake in overweight and obese subjects.

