### **1.2 Non-Clinical Summary**

In in vitro pharmacology studies, ROSE-010 and LY307161 exhibited comparable potency to each other and were both of similar potency to GLP-1 when assayed utilizing the Millipore GPCRProfiler® Service. LY307161 binds and activates the rat and human GLP-1 receptors with lower affinity than the naturally occurring peptide. From these results, it appears that the increase in activity of the peptide compared to native GLP-1 observed in vivo is not due to an increase in the intrinsic activity of the peptide, but rather to the prolonged preservation of its activity compared to native GLP-1, by virtue of its resistance to proteolytic degradation in vivo.

ROSE-010 and LY307161 have activity in in vivo animal models similar to native GLP-1, including decreasing the GI transit rate in mice. ROSE-010 at all doses had a prompt inhibitory effect on the migrating myoelectric complex, similar to GLP-1 in all animals. The action of

ROSE-010 was inhibited in the presence of Exendin(9-39)amide (a GLP-1 receptor blocker), indicating that ROSE-010 mediates the migrating myoelectric complex effect through the GLP-1 receptor.

The PK profiles of ROSE-010 were determined following SC administrations in rats and dogs. PK parameters were linear and proportional to dose. Absorption of ROSE-010 following SC administration was rapid in both rats and dogs, with time to peak concentration values of 0.25 hours in rats and <1 hour in dogs. After SC administration, ROSE-010 had a plasma half-life ranging from 0.24 to 1.68 hours at Day 91. No sexual dimorphism in PK parameters was detected in rats or dogs. There was no apparent accumulation of ROSE-010 in plasma following repeated daily SC administration.

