**Figure 1. Study Schema**

Consenting subjects will be screened for eligibility according to study-specific inclusion/exclusion criteria within 28 days prior to the first administration of study drug (Day 1).

Subjects will be admitted to the clinical pharmacology unit (CPU) on Day -1 and will remain confined to the CPU until discharge on Day 8/ET. On Day 1, subjects will be randomized in a 3:3:2 ratio to receive ROSE-010 99 mcg, ROSE-010 150 mcg, or placebo, respectively. Study drug will be administered SC once daily (30 minutes before lunch) for 7 consecutive days (Days 1 to 7). All meals served at the CPU will be standardized and controlled. Subjects will consume as much of the standardized lunch as desired, and food will be weighed prior to and after eating to assess food intake. Assessments of hunger, satiety, prospective consumption, desire to eat, palatability, and nausea will be performed. Blood samples will be collected to evaluate PK. Safety parameters will be monitored.

Subjects will be discharged on Day 8/ET. The end of study follow-up phone call will be completed 7 ( $\pm$ 2) days after the final dose of study drug.

Unscheduled procedures or visits and/or additional follow-up may be required for subjects with clinically significant abnormal laboratory findings, unresolved treatment-emergent AEs, SAEs that require follow-up laboratories and review, or clinically significant AEs.

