| 
When several assessments are required at the same time point, evaluations should be completed so that the PK sample is collected at the required time. It is understood that other assessments such as ECGs, vital signs, etc will be performed as close to the actual time as possible but may be collected earlier or later than the actual time point.
 
a. If a subject withdraws prematurely from the study for any reason, study staff should make every effort to complete the full panel of assessments scheduled for Day 8/ET. The reason for subject withdrawal must be documented in the eCRF.
 
b. Signed informed consent must be obtained before any study-related procedures are performed.
 
c. Subjects meeting eligibility criteria at Screening and Check-In will be randomized into the study pre-dose on Day 1.
 
d. Any updates since Screening will be assessed.
 
e. Any medications administered within 6 months prior to the first dose of study drug and during the study must be recorded in the eCRF.
 
f. Height will be collected at the Screening Visit only and will be used to calculate BMI at Screening only. Body weight should be measured while the subjects are wearing a gown or light indoor clothing without shoes, while fasting for at least 10 hours, and after voiding. Body weight measurements should be done in a consistent manner using a calibrated electronic scale capable of measuring weight in kilograms to 1 decimal place.
 
g. A full physical examination (including head, eyes, ears, nose, and throat; cardiovascular; respiratory; gastrointestinal; neurological; dermatological; and musculoskeletal systems) will be performed at Screening. Symptom-based physical examinations will be performed at Check-In, Day 1 pre-dose, and Day 8/ET.
 
h. Vital signs include temperature, respiratory rate, heart rate, and blood pressure. Vital signs will be performed with the subject in a seated position after at least a 5-minute seated rest. Vital signs will be assessed at Screening; Check-In; pre-dose, 1 hour post-dose, and 6.5 hours post-dose on Days 1 through 7; and on Day 8/ET. Abnormal vital signs may be repeated no more than 1 time for eligibility purposes.
 
i. A urine screen for drugs of abuse, a urine cotinine test, and a breath alcohol screen will be performed for all subjects.
 
j. The “Baseline” C-SSRS questionnaire will be administered during the Screening Period. At all other visits, subjects will be given the “Since Last Visit” questionnaire.
 
k. A serum pregnancy test will be performed for all subjects during the Screening Period and at Check-In.
 
l. A serum FSH test will be performed at Screening for subjects who are postmenopausal (ie, have experienced spontaneous amenorrhea for at least 2 years).
 
m. A test for SARS-CoV-2 will be administered to subjects at the study site on Day -1 prior to admission. Subjects testing positive for COVID-19 are not eligible for the study.
 
n. All 12-lead ECGs will be performed in triplicate approximately 1 minute apart after the subject has been resting in the supine position for at least 10 minutes. On Day 1, ECG should be performed approximately 1 hour post-dose.
 
o. Subjects are required to fast overnight (ie, no food or beverage [except water]) for at least 10 hours. All evaluations should be obtained prior to study drug administration. Abnormal laboratory tests may be repeated no more than 1 time for eligibility purposes.
 
p. Blood samples will be collected to evaluate PK on Days 1 and 7 at pre-dose (within 30 minutes prior to study drug administration) and 10, 20, 30, 45, 60, 120 and 180 minutes post-dose. The following windows will be permitted for the collection of post-dose PK samples: within ±5 minutes of the nominal time up to and including the 45 minutes sample and within ±10 minutes for samples collected 60, 120, and 180 minutes post-dose. In addition, pre-dose samples will be collected on Days 3 and 5 (within 30 minutes prior to study drug administration).
 
q. Randomization will occur after all Check-In assessments are performed and results are reviewed at pre-dose on Day 1 to confirm and verify that the subject meets all inclusion and no exclusion criteria. All subjects will be randomized to 1 of the 3 parallel treatment groups in a 3:3:2 ratio to receive ROSE-010 99 mcg, ROSE-010 150 mcg, or placebo, respectively.
 |           |                |                  |   |   |   |   |   |   |                   |                         |

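### Pre-dose PK samples fall about 24 half-lives after the last dose, so trough should be unquantifiable and swing underivable; the Day 3 and Day 5 draws would be better used at 240 minutes

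*Protocol*

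**What the plan says.** Protocol Section 1.1 gives the drug a "prolonged circulating half-life of approximately 1 hour in the human following subcutaneous (SC) injection". Section 3.1 sets the regimen: "Study drug will be administered SC once daily (30 minutes before lunch) for 7 consecutive days (Days 1 to 7".

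Footnote p of the Schedule of Events (Appendix A) fixes the PK draws. Day 1 and Day 7 each have one sample in the half hour before the dose and seven after it, timed at "10, 20, 30, 45, 60, 120 and 180 minutes post-dose". For the middle of the week the footnote adds only that "pre-dose samples will be collected on Days 3 and 5 (within 30 minutes prior to study drug administration". That makes 8 + 8 + 2 = 18 samples per subject. None is scheduled after 180 minutes on Day 7, and none on Day 8.

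Section 7.3 lists the Day 7 parameters. They include "Plasma trough concentration", AUC over a dosing interval, half-life, the terminal rate constant, clearance, an observed accumulation index, "Average concentration over the dosing interval", swing and percent fluctuation. For Day 1 it lists Cmax, Tmax, AUC to infinity and AUC to the last measurable concentration. Both lists are conditional on what the data allow. Section 1.2 reports for rats and dogs: "There was no apparent accumulation of ROSE-010 in plasma following repeated daily SC administration". SAP Section 3.4 sends all PK analysis to a separate document.

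**The concern.** The parameter list suits a drug that is still measurable when the next dose is given. On the protocol's own half-life this one is not. Trough and swing need a measurable pre-dose concentration, and the Day 3 and Day 5 draws serve only that purpose. The PK objective in Section 2.2 names Day 1 and Day 7, and the Day 7 pre-dose sample already checks for carry-over after six doses. Section 7.3 ties trough to the final dose, yet nothing is drawn at the end of that interval, so any Day 7 trough has to come from the same pre-dose sample.

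Meanwhile AUC and half-life, both named secondary endpoints in Section 7.1.2, depend on the declining limb of the curve, where sampling stops at 3 hours. At stake is the precision of a secondary objective, and two draws per subject that tell almost nothing new. No efficacy or safety result depends on it.

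**Working it through.** The plan states no PK precision figure, so there is none to reproduce.

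**Inputs from the protocol.** Human half-life about 1 h (1.1); dosing every 24 h (3.1); pre-dose draw 0 to 30 minutes before dosing; last post-dose draw at 180 minutes (footnote p). For sensitivity only: animal half-life 0.24 to 1.68 h, and animal Tmax 0.25 h in rats and under 1 h in dogs (1.2).

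**Assumptions.** One compartment with first-order absorption. Human Tmax is not given; 0.33 to 0.75 h is taken as the main range and 0.25 to 1 h as the wider one.

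**Step 1: what is left before the next dose.** The lag is 23.5 to 24 h. Fraction left = 2^(−lag / t½).

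- t½ 1 h: 2^−24 = 6.0e-8; 2^−23.5 = 8.4e-8.
- t½ 1.68 h: 24/1.68 = 14.3 half-lives, giving 5.0e-5.

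Relative to the peak, the model gives C24/Cmax of 7.5e-8 to 2.4e-7 at 1 h (Tmax 0.25 to 1 h). For trough to be quantifiable, Cmax would have to exceed the assay limit by a factor of at least 1/2.4e-7, about 4 million. At 1.68 h, C24/Cmax is 6e-5 to 1e-4, so the factor is still about 10,000.

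**Step 2: consequences for the listed parameters.**

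- Swing = (Cmax − Cmin)/Cmin. With Cmin below quantification there is no usable denominator (model value 4e6 to 1.3e7 at 1 h).
- Percent fluctuation = 100 × (Cmax − Cmin)/Cavg. Computable with Cmin = 0.
- Cavg = AUC over the interval / 24. Computable, though only the first 3 h are observed.
- Expected accumulation = 1/(1 − 2^−24) = 1.00000006 if clearance and absorption do not change over the week.

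**Step 3: AUC beyond the last sample.** With k = ln2/t½ and ka solved from Tmax = ln(ka/k)/(ka − k), the fraction beyond time T is [ka·e^(−kT) − k·e^(−ka·T)]/(ka − k). For t½ 1 h and Tmax 0.33 h, ka = 8.05 per h, so at 3 h the fraction is 8.05 × 0.125 / 7.36 = 0.137.

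| t½ | Beyond 3 h (Tmax 0.33–0.75 h) | Beyond 4 h |
|---|---|---|
| 1 h | 14%–18% | 7%–9% |
| 1.68 h | 30%–34% | 20%–22% |

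At 240 minutes the concentration is 9% to 15% of Cmax (t½ 1 h).

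**Step 4: bias in half-life from 60, 120 and 180 minutes (true value 1 h, no noise).** The three points span 2 half-lives.

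| Tmax | Fitted t½ | Estimated / true AUC to infinity |
|---|---|---|
| 0.25 h | 1.00 h | 0.997 |
| 0.5 h | 1.02 h | 1.009 |
| 0.75 h | 1.19 h | 1.03 |
| 1 h | 1.68 h | 1.12 |

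Fitting 120, 180 and 240 minutes instead gives 1.03 h at Tmax 0.75 h and 1.19 h at Tmax 1 h.

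**Step 5: precision of half-life.** Assume 15% assay noise. The SD of log half-life is about 0.15 / (k × √Σ(t − t̄)²).

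- Three points (1, 2, 3 h): Σ = 2, so 0.15/(0.693 × 1.414) = 0.153.
- Four points (1, 2, 3, 4 h): Σ = 5, so 0.15/(0.693 × 2.236) = 0.097.

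Simulation over Tmax 0.33 to 0.75 h gives 0.16 to 0.19 and 0.10 to 0.11. The precision gain comes from fitting all four points. An analyst who drops the 60-minute point gains mainly in bias (Step 4), because Σ returns to 2.

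**The case against.** The strongest reply is that little is lost. Section 7.3 lets parameters go unreported where the data do not support them, a below-limit trough is itself a result, and the named PK endpoints (Cmax, Tmax, AUC, half-life) remain obtainable. With Tmax at or below 0.5 h, the existing schedule recovers a 1 h half-life almost exactly and leaves 13% to 15% of AUC extrapolated. The 30% to 34% figure uses the top of an animal range; at its lower end, 0.24 h, 3 h is 12.5 half-lives and there is no tail to miss. The separate PK document may contain rules for below-limit values and extrapolation. The mid-week draws do check in humans that drug is absent before dosing.

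Most of this stands as a limit on size. It does not make swing derivable, because the conditional wording does not move the samples. Nor does it give the Day 3 and Day 5 draws much value once the Day 7 pre-dose sample is kept.

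Three stronger readings are tempting and not supported:

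- **Half-life and AUC to infinity cannot be estimated.** They can. At 1 h with Tmax up to 0.75 h, noise-free AUC is within about 3% of true.
- **Average concentration and percent fluctuation fall with swing.** They do not. For a drug gone by 24 h, AUC over the interval is effectively AUC to infinity, and Cmin can be set to zero.
- **The accumulation index must equal 1.** Section 7.3 calls it observed. It compares dosing days and would show a change in clearance or absorption. The statement that there is no accumulation comes from rats and dogs.

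**Conclusion.** The mismatch between parameter list and sampling times is firm for trough and swing. It needs only the stated half-life and dosing interval, and it survives every half-life tried from 0.24 to 2 h.

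The terminal-phase point is one of efficiency. Under the assumed model, 14% to 18% of AUC is extrapolated at 1 h (30% to 34% at 1.68 h) and half-life rests on about three points. Fitted half-life is materially biased only if Tmax is near 0.75 to 1 h, a possibility the documents leave open because they give no human Tmax. These figures depend on the one-compartment model and the assumed Tmax; the precision figures also depend on 15% assay noise.

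This is a cheap improvement to a secondary objective, not a defect that puts it out of reach.

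**What to change.** In footnote p, and in the PK row of the Schedule of Events, replace the Day 3 and Day 5 pre-dose draws with one 240-minute draw on Day 1 and one on Day 7. The count is unchanged: 9 + 9 = 18 per subject. Keep the Day 7 pre-dose sample as the carry-over check.

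In Section 7.3:

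- delete swing;
- state that trough is reported as below the quantification limit where it is;
- keep the observed accumulation index for Cmax and AUC;
- report half-life, AUC to infinity and the percentage extrapolated on both days.

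Average concentration and percent fluctuation need not be deleted, provided the plan says Cmin is set to zero when below the limit. The PK analysis document should state which points enter the terminal fit.

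The cost is a minor protocol amendment. Subjects are already confined to the unit, and a 4-hour injection-site check already exists on Day 1. Two downsides should be stated: there is no mid-week pre-dose check, and the gain depends on the 240-minute level being quantifiable. The sponsor should confirm the latter against the assay limit before amending.
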